3.3 Statistical Analysis Method

Statistical analysis using SPSS Software (version 21. Inc. Chicago, IL USA) Wilcoxon sign rank test was used to prove the effects of endurance exercise on nrf2 mRNA expression gene and VO_{2max}. Linear regression test and Spearman Rank to analyze the correlation of the nrf2 gene mRNA with VO_{2max} and the Mann Whitney test to prove changes in retention VO_{2max}.

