Indonesian Hajj Health Officers are health workers assigned by the Minister of Health of the Republic of Indonesia to provide services, guidance, and health protection to pilgrims during the Hajj pilgrimage, not it is only sufficient to have work competence in terms of knowledge, skills and work attitudes that are in accordance with established standards, but it is highly demanded to have excellent physical endurance. An Indonesian Hajj Health Officer is required to have 3 (three) abilities in carrying out his duties and responsibilities in the health sector, namely (a) managerial ability, (b) skill ability and (c) excellent physical ability. Excellent physical ability is one of the main keys to success in providing health services to Indonesian Hajj pilgrims, this is possible because the number of Indonesian Hajj pilgrims is very large and the length of time serving Indonesian Hajj Health Officers for approximately 39 days for TKHI and 76 days for PPIH. The physical fitness of a Hajj Health Officer is required in addition to being in general fitness, they must also be demanded for specific physical fitness. Standardization of individual physical fitness in general can be measured by the $VO_{2\max}$ level is one of the markers of physical fitness and an increase in $VO_{2\max}$. Regular exercise can increase of $VO_{2\max}$ levels. So the higher one's $VO_{2\max}$, also has good endurance. Endurance exercise consists of two groups, namely endurance cardio respiration (general) and muscle endurance (local). For measurement of cardiorespiratory endurance by $VO_{2\max}$. Some of the results of research in the field biomolecular of genetic markers for endurance, one of which is the nrf2 gene, also known as GA-binding protein transcription factor β sub unit (GABPB1), which is a transcription factor in mitochondrial biogenesis. Mitochondrial Biogenesis and nucleus expressed by one of the nrf2 mRNA genes encoded by the GABPB1 gene, located on chromosome 15q212.

2. Objectives

The aim of the research was to examine the effects of Endurance Exercise on the Expression of the mRNA Nrf2 gene and Level of $VO_{2\max}$ of Indonesian Hajj Health Officers.

3. Methods

This study was a single group quasy experiment that took place in two locations the Makassar Health Training Center and Makassar Haji Sudiang Dormitory.

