3.1 Participant

Participants are Prospective Indonesian Hajj Health Officers as many as 30 participants consisting of 17 men and 13 women. Criteria for inclusion of participants include: (a) Participants from the Nurse profession aged 30 - 39 years (b) Pass the selection of candidates for Indonesian Hajj Health Officers (c) Understand the physical training program instructions in the rockport method (d) willing to participate in activities and all research provisions . Participants who (a) had a history of coronary heart disease, asthma; (b) not approved by the doctor to participate in the study due to a medical condition, excluded from the study.

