3.2 Desain and measure

3.2.1 Exercise Protocol

Subject ($n = 30$), measured $VO_{2\max}$ level 3 times using the Multistage Fitness technique Test (MFT) Bleep Test method (level and feedback) before and after the 1600 meter running exercise duration 20-30 minutes 3 times a week with a frequency of exercise 16 times, then measuring $VO_{2\max}$, 1 week after exercise without running intervention.

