3.2.2 VO_{2max} Measurement

Level value and feedback from the Bleep test, then the value is converted into the VO_{2max} based on the level achievement and feedback obtained, then the VO_{2max} value is grouped into the form of levels including special, excellent, good, moderate, less and very less.

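### Section 3.3 gives the signed-rank test a causal conclusion that one exercised group without a control cannot support; a significant result shows only a before–after change

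*Combined protocol and SAP*

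**What the plan says.** Section 3.3 (Statistical Analysis Method) gives the purpose of the main test: "Wilcoxon sign rank test was used to prove the effects of endurance exercise on nrf2 mRNA expression gene and VO_{2max". Section 2 (Objectives) is worded in the same direction: "The aim of the research was to examine the effects of Endurance Exercise on the Expression of the mRNA Nrf2 gene", and it goes on to name VO2max as well.

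The design is stated openly in section 3: "This study was a single group quasy experiment". Section 3.1 gives the size, "as many as 30 participants consisting of 17 men and 13 women". Section 3.2.1 has all of them train and be tested "before and after the 1600 meter running exercise duration 20-30 minutes 3 times a week", for 16 sessions. A third VO2max test follows "1 week after exercise without running intervention".

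Section 3.2.2 converts the bleep-test result to a VO2max value, after which the "value is grouped into the form of levels including special, excellent, good, moderate, less and very less". Section 3.3 does not say whether the converted value or the six levels are tested. Section 3.2.3 describes the nrf2 assay, with GAPDH as the housekeeping gene, but no section says when the samples were taken.

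No section describes a control group, a repeat baseline, a familiarisation test, or any limit on what a significant before–after result may be taken to mean.

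**The concern.** The signed-rank test asks whether paired changes are centred on zero. Rejecting that hypothesis says that values moved, not why they moved. Section 3.3 nevertheless assigns the cause to the training programme.

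For VO2max there are obvious rival explanations. The bleep test is volitional, so a second attempt may go better through familiarity or greater effort. For nrf2 mRNA, anything else that changed over the same period is a rival.

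The stake is the trial's headline conclusion. With the test's purpose worded this way and no stated limit, a small p-value is set up to be reported as an effect of exercise, when it supports only a statement about change.

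**Working it through.** The plan states no significance level, sidedness, power, effect size or SD, so it offers no figure to reproduce. The one arithmetic check available agrees: 17 + 13 = 30. The point rests on setting the sections side by side; the simulation afterwards is only an illustration.

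**Step 1: what the signed-rank comparison contains.**
- Groups: one, and everyone exercises (sections 3 and 3.2.1).
- VO2max measurements before training: one (3.2.1).
- VO2max measurements directly after the programme: one (3.2.1).
- Interval: 16 sessions at 3 a week is 16/3 ≈ 5.3 weeks, if the schedule is kept.
- nrf2 mRNA: before-and-after sampling is inferred from the choice of a paired test; it is not stated.

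**Step 2: what that comparison can identify.** Write each person's change as D = E + F + T + error. Here E is the exercise effect, F is familiarity or effort on retest (VO2max only), and T is any other change over the interval. The test concerns the centre of D. With one group, E, F and T enter only as a sum. A control group would estimate F + T, and a repeat baseline would inform F. The plan has neither, so E is not separately estimable.

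**Step 3: whether the third VO2max test supplies what is missing.** It is taken in the same people after training, so it is neither a control nor a second baseline. It is described for VO2max only. Section 3.3 assigns retention to a different test (Mann-Whitney), so the third value is not part of the signed-rank comparison. A fall at that visit would count a little against pure familiarity, but it would not exclude differences in effort.

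**Step 4: illustration of size.** Assumptions, none of them from the documents: two-sided 5% level, normally distributed paired changes, E = 0, and a non-exercise shift F + T expressed in SDs of the paired change. For n = 30 the rank sums total 30 × 31/2 = 465. The exact test rejects at W ≤ 137 or W ≥ 328 (465 − 137 = 328), with exact size 0.0497. With 500,000 simulated studies per shift:

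| Assumed non-exercise shift (SD of change) | Share of studies with p<0.05 |
|---|---|
| 0.2 | 0.179 |
| 0.3 | 0.343 |
| 0.38 | 0.503 |
| 0.5 | 0.735 |

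A separate run with the normal approximation (20,000 studies per shift) gave 0.185, 0.343 and 0.740 at 0.2, 0.3 and 0.5 SD. In that run, comparing changes with a hypothetical unexercised group (30 v 30, same shift in both, Mann-Whitney) stayed between 0.046 and 0.049 at those shifts.

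**Step 5: converted value or six levels.** If the six levels were tested, the same shifts of 0.2, 0.3 and 0.5 SD would give p<0.05 in about 11–16%, 19–30% and 47–68% of studies. The range covers assumed before–after correlations of 0.5 to 0.9 and two assumed sets of cut-points. Grouping makes the test less sensitive to a shift and leaves no natural size of change to report.

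**Step 6: precision of the proposed estimate.** For 30 continuous normal changes, the 95% interval around the Hodges-Lehmann estimate had a mean half-width of 0.379 SD of the paired change and coverage of 0.954 (4,000 simulations).

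**The case against.** The best reply is that this is mostly wording. Section 3.3 uses the same verb for the Mann-Whitney test, so it may simply mean that a hypothesis is tested, and section 3 tells every reader that there is one group. The data, the test and the p-value would be the same after the fix. This stands as far as the verb goes. It does not dispose of the point, because the phrase still names exercise as the cause of whatever is found, and disclosing a design is not the same as limiting the conclusion drawn from it.

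A second reply is that the third VO2max test adds a withdrawal phase. It does, and any fair account of the design should say so. For the reasons in Step 3, it gives weak supporting evidence for one of the two outcomes.

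A third reply is that the percentages show only that a test of change detects change, under shifts that nobody has measured. That is right. The documents indicate no drift of any size, and the conclusion does not depend on the figures.

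A reader might also infer that the signed-rank test is the wrong test, that its type I error is inflated, or that the trial is invalid without a control arm. The documents support none of these. It is a suitable paired test of before–after change. The percentages are not errors under its own null hypothesis. An uncontrolled study can legitimately report a within-person change.

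**Conclusion.** The concern holds as a mismatch between the design and the conclusion assigned to the test, in section 3.3 and, by the same wording, in the section 2 objective. A significant signed-rank result in this trial supports the statement that values differed before and after the programme. It does not support attributing the difference to exercise.

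This rests on the documents alone: one exercised group, one VO2max measurement before training, no control and no stated limit. Only the illustrated size rests on assumptions (shift, two-sided 5% level, normal changes). Under these, a non-exercise shift of 0.38 SD of the paired change would produce a significant result about half the time. It should not be read as evidence that such a shift occurred, or that exercise had no effect.

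The nrf2 part carries an added condition, because paired sampling for that outcome is inferred and not stated.

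**What to change.** 1. In section 3.3, replace the causal clause of the signed-rank sentence so that the test is used to *test and estimate the within-person change from before to after the programme in* nrf2 mRNA and VO2max.
2. State that the converted VO2max value is tested, not its six levels. Report the Hodges-Lehmann estimate of the paired change with a 95% CI, using a method that allows for ties and zero changes. The converted values may be discrete if they come from level and shuttle counts, in which case the half-width in Step 6 is only approximate.
3. Do the same for nrf2 mRNA if samples were taken before and after, on one stated scale (for example GAPDH-normalised log expression), because the estimate depends on the scale.
4. Add one sentence that applies to both section 3.3 and the section 2 objective: *Because there is no control group, a significant result will be concluded as a pre-post change and not as a demonstrated effect of exercise; the one-week post-exercise VO2max measurement is supportive only.* With that sentence in place, the objective need not be rewritten.

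The cost is a less favourable claim and two extra intervals. No participants, visits or assays are added. The change does not alter how often p<0.05 occurs; it alters what such a result may be said to show.

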3.2.3 Measurement of mRNA NRF2 Gene Expression

RT-PCR analyzes human RNA in the nrf2 RNA sample as the target gene and GAPDH is selected as the housekeeping gene. Samples were preserved in nuclease free water (Norgen biotech, Inc.), and RNA was extracted using the RNA isolation kit "RNAPrep pure kit for blood" (Tiangen Biotech, Beijing). cDNA is cleaned using the "iScript cDNA synthesis kit" (Bio-Rad Laboratories, Inc.) cDNA kit and store at -20°C until analyzed by RT-PCR. RT-PCR is run on CFX96 touch (Bio-Rad Laboratories, Inc.) using the QPCR master mix "Ssofastevagreen supermix" (Bio-Rad Laboratories, Inc.). Specific gene primer pairs are described as follows:

Forward: GAGAGCCCAGTCTTCATTGC;

Reverse NRF2 Primary: TTGGCTTCTGGACTTGGAAC.

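### The planned nrf2–VO2max regression and Spearman correlation name no covariate in a sample of 17 men and 13 women; sex should be in the model and one main association named in advance

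*Combined protocol and SAP*

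**What the plan says.** Section 3.3 gives the association one clause: "Linear regression test and Spearman Rank to analyze the correlation of the nrf2 gene mRNA with VO_{2max". It names two methods. It gives no covariate, no stratification, no measurement occasion, no choice between levels and changes, and no order between the methods. No other section fills these gaps.

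The relevant facts elsewhere are:

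- Section 3.1: the sample is "as many as 30 participants consisting of 17 men and 13 women". Profession and age are restricted; sex is not, and it is not used again.
- Section 3.2.1: VO2max is measured before training, after it, and again "1 week after exercise without running intervention".
- Section 3.2.2: the bleep-test result is converted to a numeric VO2max and also grouped into six categories. The plan does not say which form enters the association.
- Section 3.2.3: expression is measured with "nrf2 RNA sample as the target gene and GAPDH is selected as the housekeeping gene". Sampling times are not given, but the signed-rank test that section 3.3 assigns to nrf2 needs paired samples.
- Section 2: the objective is the effect of training on nrf2 expression and on VO2max. The link between the two is not part of it.

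No alpha, power or sample-size calculation is stated.

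**The concern.** A bivariate correlation of levels in a mixed-sex sample combines two things: the link among people of the same sex, and the difference between the male and female averages. If both variables differ by sex, the second part alone produces a correlation. A reader would probably take a significant result to mean that people with more nrf2 expression have higher VO2max, when it may show only that men and women differ on both.

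If only VO2max differs by sex, no spurious link arises. The sex gap then acts as unexplained variance, and a real within-sex link is easier to miss.

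A smaller, separate issue is that levels before training, levels after it, and changes all fit the sentence in section 3.3. The analysis reported could therefore be picked after the results are seen.

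**Working it through.** **Inputs from the documents.** 17 men and 13 women; 17 + 13 = 30, which agrees with the stated total. There is no other figure in the plan to reproduce.

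**Assumptions.** Two-sided 5% level; normal data; sex gaps in within-sex SD units, dV for VO2max and dG for nrf2. Simulated rates use the 17/13 split and 40,000 trials per cell.

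**Step 1. Correlation created by sex alone (levels, no within-sex link).** With p = 17/30 and q = 13/30, pq = 221/900 = 0.2456, and

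r = pq·dV·dG / √[(1 + pq·dV²)(1 + pq·dG²)].

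- dV = 1, dG = 0.5: 0.1228 / √(1.2456 × 1.0614) = 0.107.
- dV = 2, dG = 1: 0.4911 / √(1.9822 × 1.2456) = 0.313.
- dG = 0: r = 0.

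**Step 2. How often the pooled Spearman test is significant (levels, no within-sex link).**

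| nrf2 gap | VO2max gap 1 SD | 1.5 SD | 2 SD |
|---|---|---|---|
| 0 | 5.0% | – | 4.8% |
| 0.25 SD | 6.0% | – | 7.4% |
| 0.5 SD | 8.6% | 12.2% | 15.4% |
| 1 SD | 18.3% | 31.5% | 43.0% |

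A dash marks a cell that was not run. A separate 20,000-run simulation gave similar figures for unadjusted linear regression: 8.9% at 1/0.5 and 41.2% at 2/1. With sex included, the linear and partial Spearman tests both stay at 4.8–5.2%.

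**Step 3. Power for levels when only VO2max differs by sex (within-sex r 0.5).** The pooled correlation shrinks to 0.5 / √(1 + pq·dV²), which is 0.448, 0.401 and 0.355 at dV = 1, 1.5 and 2. Fisher's approximation, Φ(atanh(r)·√27 − 1.96), then gives about 71%, 60% and 49%, in line with the simulated linear figures:

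| VO2max gap | Linear, no sex | Linear + sex | Spearman, no sex | Partial Spearman |
|---|---|---|---|---|
| 1 SD | 71.6% | 81.3% | 65.2% | 75.0% |
| 1.5 SD | 60.5% | 81.3% | 53.2% | 74.3% |
| 2 SD | 48.3% | 81.2% | 41.1% | 74.4% |

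Compared method with method, the gain is about 10 points at a 1 SD gap and 33 points at 2 SD.

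**Step 4. If changes are used instead.** A constant male–female offset cancels in the difference, so the null rejection rate is about 5% with or without the sex term. Sex matters only if training responses differ. With both response gaps at 0.5 SD of change the unadjusted rate is 6.1%, and at 1 SD it is 18.9%; adjusted, it is 4.9–5.1%. If only one response differs (0.5/0) it is 5.0%.

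**Step 5. Open choice among before, after and change under a complete null.** Three sets of pre–post correlations were assumed (VO2max/mRNA 0.8/0.5, 0.9/0.7, 0.7/0.3). At least one p < 0.05 among three Spearman tests occurs in 13.5–14.1% of trials, and by either test in 17.3–18.1%. With one fixed pair of variables and either test the rate is about 6.5–7%. These runs leave out the third VO2max occasion.

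**Step 6. Cost of the sex term.** The detectable r at 80% power is tanh(2.80/√26) = 0.50 with sex, against tanh(2.80/√27) = 0.49 without. Simulated power at r 0.5 with no sex gap falls from about 83% to 81–82%.

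**The case against.** - **The pooled correlation is not wrong in itself.** If both variables differ by sex, it is truly non-zero, and rejecting zero answers the marginal question correctly. This stands. The 9–43% are errors only for a within-sex reading. Section 3.3 states neither question, so the plan should say which one it means.
- **The sex gaps are assumed.** This stands too. Results run from 5% to 43% depending on values that the documents do not give. A reader might infer that sex confounding has been shown here; it has not. The word unadjusted is also an inference from silence, although Spearman as named takes no covariate.
- **The large figures concern levels.** Correct. For changes the sex term is a precaution against unequal training responses, not the repair of a demonstrated fault. Section 3.3 does not commit to changes, so the issue for levels remains open.
- **The 14% and 18% need selective reporting.** Correct, and nothing in the documents indicates selection. They are upper figures for choosing after the fact, not the plan's error rate.
- **The association is secondary.** Agreed. This limits the weight of the point but does not remove it, since section 3.3 still plans to report the association.

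**Conclusion.** The point holds as an inexpensive improvement to a secondary analysis. For levels, leaving sex out lets a sex contrast enter the pooled correlation when both variables differ by sex, and loses power when only VO2max does. Adding sex protects against both, whichever gaps turn out to be true. The size depends on the assumed gaps, normal data and a two-sided 5% level.

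Two stronger readings are not supported. One is that changes are the right main analysis and levels the wrong one. That depends on the question: a change analysis cannot detect a link that exists only between stable levels, and the background section presents nrf2 as a marker of endurance, which can be read as a between-person question. The other is that the before/after comparison is compromised. The signed-rank tests compare each person with themselves and are untouched by this point.

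**What to change.** In section 3.3:

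1. Fit a linear regression of numeric converted VO2max on log GAPDH-normalised nrf2 expression, one row per person, with sex as a covariate.
2. Use the sex-adjusted partial Spearman correlation of the same two variables as the supporting rank analysis.
3. Name in advance either one occasion or the before-to-after change as the main association, and state which nrf2 sample or samples it uses. The choice is the sponsor's. If change is chosen, describe the sex term as a precaution against different training responses.
4. Label the association exploratory, because section 2 does not include it.

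The cost is wording and one degree of freedom, with power at r 0.5 falling from about 83% to 81–82% if there is no sex gap. Sex is already recorded. Adjustment does not remedy the small sample: with 30 people and a sex term, only correlations of about 0.5 or more reach 80% power.

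### Retention of VO2max is assigned the independent-samples Mann-Whitney test in a one-group study; a paired test on the 1-week minus post-training differences is needed

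*Combined protocol and SAP*

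**What the plan says.** The Methods section describes the design: "This study was a single group quasy experiment". Section 3.1 gives its size as "30 participants consisting of 17 men and 13 women". Under section 3.2.1 every subject has VO2max measured "level 3 times using the Multistage Fitness technique": before the running programme, after it, and again "1 week after exercise without running intervention". The third measurement is the only one that bears on retention.

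Section 3.3 then gives two different tests for within-person change. For the training effect, "Wilcoxon sign rank test was used to prove the effects of endurance exercise". For retention, it names "the Mann Whitney test to prove changes in retention VO_{2max". It does not say which two samples the Mann-Whitney test compares.

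Section 3.2.2 adds a second ambiguity. The bleep-test result is converted to a VO2max value, and that "value is grouped into the form of levels including special, excellent, good, moderate, less and very less". Section 3.3 does not say whether the value or the six levels are analysed.

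**The concern.** Mann-Whitney assumes two independent samples. With one group measured repeatedly, the obvious retention comparison (1 week versus end of training) sets each person against himself or herself. An unpaired test leaves the stable differences between people in the error term, whereas a paired test removes them. The same paragraph already uses a paired test for the training effect, so the plan handles two within-person changes in incompatible ways.

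What is at stake is the retention conclusion. If repeat values correlate positively, the unpaired test rejects too rarely. A significant loss would not be a false alarm caused by the test, but a real loss of modest size could easily go undetected, and a non-significant p-value could then be reported as fitness retained.

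**Working it through.** **Inputs from the documents.** One group; n = 30; three VO2max measurements per person; Mann-Whitney for retention; Wilcoxon signed-rank for the training effect.

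**Inputs the documents do not give, assumed here.** Two-sided alpha 0.05; normal data with equal SD at both times; within-person correlation ρ from 0.3 to 0.95 (with ρ = 0 as a check); loss from 0 to 0.8 between-person SD; all 30 people measured at both times. There is no stated power or effect size to reproduce.

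**Step 1: what ignoring the pairing does.** For a difference in means, in SD units:

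- unpaired SE = √(2/30) = 0.258, whatever ρ is;
- paired SE = √(2(1−ρ)/30);
- ratio = 1/√(1−ρ) = 1.20, 1.41, 1.83, 2.24, 3.16 and 4.47 at ρ = 0.3, 0.5, 0.7, 0.8, 0.9 and 0.95.

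The unpaired comparison therefore needs an observed difference of about 1.96 × 0.258 = 0.51 SD to reach significance, however reproducible the measurement. A true loss of 0.5 SD sits almost on that threshold and is found about half the time. A true loss of 0.25 SD lies well below it.

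Hand check at ρ = 0.5 and a loss of 0.25 SD, where the paired SE is √(1/30) = 0.183:

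- unpaired power ≈ Φ((0.25 − 0.506)/0.183) = Φ(−1.40) ≈ 8%;
- paired power ≈ Φ(0.25/0.183 − 1.96) = Φ(−0.59) ≈ 28%.

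**Step 2: simulation with the two rank tests.** 10,000 trials per cell, 30 bivariate-normal pairs, normal approximation with tie correction and no continuity correction. Power is Mann-Whitney v signed-rank.

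| ρ | Mann-Whitney type I error (nominal 5%) | Power, loss 0.25 SD |
|---|---|---|
| 0.3 | 2.1% | 11% v 19% |
| 0.5 | 0.8% | 8% v 25% |
| 0.7 | 0.2% | 4.5% v 39% |
| 0.8 | <0.1% | 2.6% v 53% |
| 0.9 | <0.1% | 1.0% v 83% |
| 0.95 | <0.1% | 0.3% v 98% |

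Larger losses:

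| Loss | ρ = 0.5 | ρ = 0.7 to 0.95 |
|---|---|---|
| 0.4 SD | 27% v 55% | 14–22% v 76–100% |
| 0.5 SD | 45% v 73% | 44–49% v 92–100% |
| 0.8 SD | 91% v 98% | 96–99.9% v 100% |

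At ρ = 0 the tests perform alike (loss 0.25 SD: 15% v 15%), so pairing costs essentially nothing.

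**Step 3: does the outcome scale change this?** With both measurements cut into six ordered levels, assumed equally frequent after training, the pattern holds:

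- loss 0.25 SD: 8% v 22% at ρ = 0.5, and 0.4–4.8% v 33–87% at ρ = 0.7 to 0.95;
- loss 0.5 SD: 39–41% v 85–100% at ρ = 0.7 to 0.95.

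**Step 4: the other possible reading.** The only independent subgroups in the documents are the 17 men and 13 women. Mann-Whitney on their change scores would be legitimate, but section 3.3 states no such comparison. It would ask whether the sexes differ in their change, not whether the group lost fitness.

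**The case against.** The strongest reply is that the text proves only an undefined comparison, not a wrong one. Mann-Whitney could have been meant for change scores between subgroups. That stands as a point about certainty: the paired reading is an inference. It does not rescue the plan, because the subgroup comparison is stated nowhere and would leave the group's retention untested.

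A second reply is that a test whose type I error stays below 5% is inefficient rather than invalid. It is true that the error is on the conservative side. But the independence assumption behind the p-value fails, so its nominal level does not describe it, and the size of the departure depends on a correlation the plan does not give.

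Third, the signed-rank test also misses small losses. At 0.25 SD it misses 81% at ρ = 0.3 and 75% at ρ = 0.5, and at 0.1 SD its power is only 7% to 38% for ρ from 0 to 0.95. The most striking contrasts need ρ of 0.9 or more. All of this stands. The fix recovers power without guaranteeing detection, which is why an interval estimate is needed as well as a test.

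Finally, retention is not in the stated objective, the training effect already has a paired test, and the plan makes no explicit claim that non-significance means retention. This limits the reach of the harm but does not make the named test suit the design.

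**Conclusion.** The concern holds: section 3.3 is wrong as written on this point and must be corrected. The design supplies no two independent samples for a test of group retention. On the natural reading the test discards the pairing; on the only alternative it answers a different question.

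The mismatch between test and design does not depend on any assumed value. Its numerical size does: it rests on normal data, complete pairs, two-sided 0.05 and an assumed positive correlation, and no cell in the tables can be called the expected one. Within those scenarios, Mann-Whitney detects a loss of 0.25 SD in at most 11% of trials and misses a loss of 0.5 SD about half the time. It rarely misses a loss of 0.8 SD at ρ of 0.5 or more. The consequence is a missed loss, not a spurious one, and it is confined to the retention result.

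**What to change.** In section 3.3:

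1. Name the two measurements compared for retention: the 1-week value and the post-training value.
2. Replace Mann-Whitney with the Wilcoxon signed-rank test on each participant's 1-week minus post-training difference, using the converted VO2max value and not the six grouped levels.
3. Report the paired Hodges-Lehmann difference with its 95% CI, and base any statement about retention on that interval, not on a non-significant p-value. If fitness is to be declared retained, the plan must also state in advance the largest loss compatible with that statement, because the interval alone does not settle it.

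If a comparison between independent subgroups was also intended, state the groups and list it as a separate analysis; it cannot replace the paired one.

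The cost is one or two sentences of analysis wording. No new data are needed.
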